3.2. Secondary Endpoint(s)

The AIR per participant will be calculated as:

The number of infusions received x 365.25 days/number of days during the observation time period while participant received prophylaxis factor replacement therapy in the usual care setting from baseline visit (Day 1) to end of study (date of study completion or discontinuation, whichever is earlier).

Similarly as ABR (Section 3.1), the retrospectively collected AIR per participant will be equal to number of infusions within the last 12 months collected in the Hemophilia History form.

AIR combining retrospective and prospective data will be calculated as:

$$\frac{(\text{Number of infusions from baseline visit (Day 1) to end of study} + \text{Number of infusions collected in Hemophilia History form})}{(\text{Number of days from baseline visit (Day 1) to end of study} + 365.25)/365.25}$$

The annualized factor consumption will be calculated as:

The total factor replacement therapy consumption (in international unit [IU] and dose) x 365.25 days/number of days during the observation time period while the participant received factor prophylaxis replacement therapy in the usual care setting from baseline visit (Day 1) to end of study.

The number of bleeding episodes will be annualized using the same methods as the primary endpoint by spontaneous, traumatic and overall (treated and untreated) as defined in Protocol Appendix 2.

3.3. Exploratory Endpoint

For hemophilia B participants, AAV-Spark100 nAb status will be measured from the blood samples collected at the screening visit. For hemophilia A participants, AAV6 nAb status will be measured from the blood samples collected at the screening visit. The established threshold for AAV-Spark100 and AAV6 nAb status is 1:1 and 1:4, respectively.

3.4. Baseline Variables

Demographics, medical, surgical and hemophilia history (including the number of bleedings and infusions during the 12 months prior to enrollment, if collected) collected prior to the start of the prospective data collection will be summarized.

3.5. Safety Endpoints

3.5.1. Adverse Events

The adverse events (AE) reporting period in this study is defined as the time from the participant's informed consent through end of study visit. Only SAEs, protocol defined AESI, and non-serious events leading to study discontinuation or unscheduled visits were reported; therefore, summaries of C0371004 will be restricted to these endpoints.

The events of special interest (ESI) include but are not limited to: inhibitor against FIX or FVIII, thrombotic events, and FIX or FVIII hypersensitivity reactions. The 3-tier AE approach will not be applied.

In this study, AE will not be defined as treatment emergent or not since this is a non-investigational drug study.

All AE data will be coded using the most updated version of MedDRA dictionary.

[figure not shown]
3.5.2. Laboratory Data

Laboratory data will not be reported as there are no safety laboratory measurements required during the prospective data collection phase of the protocol besides the procedures performed in the usual care setting.

4. ANALYSIS SETS

Data for all participants will be assessed to determine if participants meet the criteria for inclusion in each analysis population. There is no randomization or blinding in this study. The analysis population will be defined separately for the hemophilia B cohort and the hemophilia A cohort, unless otherwise specified.

The various follow-up periods for participants enrolled under Protocol Amendment 5 (PA#5) (or later) and prior to PA#5 are shown below in [Figure 2](#).

Figure 2. Participants' follow-up scenarios

4.1. Full Analysis Set (Immunity Analysis Set)

The immunity analysis set is defined as all participants who signed an informed consent form (ICF) and had their blood sample collected and assayed for AAV-Spark100 or AAV6 immunity testing.

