4.4. Screen Failures

Screen failures are defined as participants who consent to participate in the clinical study but are not subsequently entered in the study. A minimal set of screen failure information is required to ensure transparent reporting of screen failure participants to meet the Consolidated Standards of Reporting Trials (CONSORT) publishing requirements and to respond to queries from regulatory authorities. Minimal information includes demography, screen failure details, eligibility criteria, and any serious adverse event (SAE).

Study participants who do not meet the criteria for participation in this study (for example, screening laboratory results and/or FibroScan results) and are deemed a screen failure, may be rescreened, because these laboratory and/or FibroScan results can change over time. The repeated central laboratory and/or FibroScan results must be available prior to the Baseline Visit and be within range for the participant to be eligible. Rescreened participants are required to sign a new ICD and will be assigned a different participant number.

Note: Study participants who are not deemed a screen failure, and have a test value (eg, central laboratory and/or FibroScan) that is outside the range specified by the exclusion criteria, repeated by the central laboratory to determine eligibility. However, the new result must be available prior to the Baseline Visit and be within range for the participant to be eligible.

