5.1. Allocation to Treatment

The investigator's knowledge of the participant's current FIX or FVIII prophylaxis replacement therapy regimen should not influence the decision to enroll a particular participant or affect the order in which participants are enrolled. The study will be conducted as an open-label and non-randomized trial.

The investigator will assign all participant identification numbers sequentially to their participants as they are screened for the study. This identifying number will be retained throughout the study and remains confidential. A participant number must never be reassigned or reused for any reason. The investigator must maintain a confidential study log linking the participant number to the participant's name.

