6. STUDY PROCEDURES

Remote Baseline Visit: If permitted by local regulations, the baseline visit may be conducted as a remote visit, where participants do not go to a site to complete the baseline visit but the baseline visit can be conducted by the investigator and/or site staff via telehealth (eg, audio, video, video conferencing software). The end of study visit will be conducted on site.

6.1. Screening Visit – Screening Phase to Determine nAb Status and Eligibility into Data Collection Phase (Day -42 to Day -1)

All screening procedures must be completed within 42 days of Day -1. No study-related procedures may be performed until the Informed Consent process is completed. The following procedures will be performed prior to participant enrollment:

- Obtain written informed consent. Collect and record participant demography (including date of birth (month and year), sex/gender, race, and ethnicity).
- Collect medical history.
- Collect hemophilia history including (but is not limited to) date of diagnosis, severity, history of inhibitor (FIX inhibitor for hemophilia B participants or FVIII inhibitor for hemophilia A participants), family inhibitor history, gene mutation (if available), number of exposure days, number of bleeds and infusions within the last 12 months (where available), and current FIX or FVIII treatment and regimen.
- Collect vital signs (temperature [°C], blood pressure [sitting], pulse and respiration), body weight (kg) and height (cm).
- Collect blood sample for both nAb against AAV-Spark100 (hemophilia B) and AAV6 (hemophilia A) nAb assessment (central laboratory). In the hemophilia B population, the samples collected during the screening visit may be used to test nAb against AAV6, as well as testing for antibodies against additional AAVs, at the end of the study (Note: Hemophilia B participants screened prior to Amendment 5 will be reconsented prior to testing their previously collected samples for nAb against AAV6, as well as testing for antibodies against additional AAVs). The nAb result against AAV6, as well as antibodies against additional AAVs, will not be shared with the hemophilia B participants. In the hemophilia A population, the samples collected during the screening visit may be used to test nAb against AAV-Spark100, as well as

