testing for antibodies against additional AAVs, at the end of the study. The nAb result against AAV-Spark100, as well as antibodies against additional AAVs, will not be shared with the hemophilia A participants.

- Approximately 20 mL (4 teaspoons) of blood.
- Samples will be collected for the following tests (central laboratory): Factor IX/VIII activity (if there is no documentation), HBV, HCV, liver fibrosis (FibroScan OR FibroTest/FibroSURE), and HIV serology (viral load and CD4 count for HIV positive participants only), only if there is no documentation within the last 12 months prior to screening (6 months for HCV):
 - Approximately 20 mL (4 teaspoons) of blood.
 - Review inclusion and exclusion criteria.
 - Record adverse events (reference [Section 8.1](#) for protocol specified adverse event reporting) in addition to any research-related injury adverse event arising through screening blood draw collection.
 - Record concomitant treatments (drug and non-drug).

In the absence of a documented FIX:C or FVIII:C level (according to the underlying disease) participants will observe a minimum 72-hour FIX or FVIII washout for recombinant or plasma derived products or a minimum of 5-10 days or longer for extended half-life products prior to the baseline visit. Depending on when the last FIX or FVIII dose was administered before the beginning of the FIX or FVIII washout, an interval longer than 72 hours or 5-10 days may be needed. The screening visit window may be extended, upon consultation with the sponsor's medical monitor. Reason for the extension must be recorded in the source documents. If a participant sustains a bleed requiring treatment during the >72-hour or >5-10 day FIX or FVIII washout, the necessary treatment should be administered using the participant's usual FIX or FVIII replacement product. Once the bleed has been adequately treated, the screening visit must be rescheduled, and must be preceded by a new >72-hour or >5-10 day FIX or FVIII washout prior to baseline visit (Day 1), upon the availability of the nAb laboratory test results, the study site will notify participants of their nAb laboratory test results via a telephone call.

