Hemophilia B Populations: Neutralizing antibodies against AAV-Spark100 transgene product positive participants will be contacted to explain what the implications of being nAb positive are and subsequently discontinued from further participation in the study. Neutralizing antibodies against AAV-Spark100 negative participants will be contacted to schedule a baseline visit to issue their electronic diary and continue on with the data collection phase.

Hemophilia A Population: Neutralizing antibodies against AAV6 positive participants will be contacted to explain what the implications of being nAb positive are and subsequently discontinued from further participation in the study. Neutralizing antibodies against AAV6

negative participants will be contacted to schedule a baseline visit to issue their electronic diary and continue on with the data collection phase.

For both the hemophilia B and hemophilia A populations, site staff should conduct electronic diary training with the study participant at the screening visit if the baseline visit will be conducted remotely.

- For Diary and Device Training at Screening Visit:
 - Site to provide Contact Authorization Form (CAF) for study participant to review and sign.
 - The site will need to log into mPal and add the study participant. Please activate the device using the Activation Code (found on the mPal study participant profile in lime green letters). Once Trial Guide is activated, the study participant can navigate to the “Diary” tab and complete the “Training Infusion Log” and the “Training Bleed Log”.
- Study Participant Eligible (nAb negative):
 - The site to ship the activated device to the study participant’s home prior to the baseline visit.
- Study Participant Ineligible (nAb positive):
 - Please log in to mPal, find and click on the study participant ID and click “Archive”. Select “Screen fail” as the reason for archival. Clear all push notifications from the device and confirm that the Trial Guide mobile application has the “Activation Code” screen showing.

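### Could rescreening under a new participant number count one person twice in the exploratory nAb positive rate?

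*SAP*

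**What the plan says.** The nAb positive rate is the exploratory endpoint. SAP 4.1 takes as its population "all participants who signed an informed consent form (ICF) and had their blood sample collected and assayed for AAV-Spark100 or AAV6 immunity testing". SAP 6.3.1 analyses the whole of that set by cohort, overall and by region, with a two-sided 95% Clopper-Pearson interval. Its numerator is nAb-positive participants and its denominator is sampled participants.

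Protocol 4.4 lets a screen failure be screened again: "Rescreened participants are required to sign a new ICD and will be assigned a different participant number". Protocol 5.1 adds that "A participant number must never be reassigned or reused for any reason", and that the investigator "must maintain a confidential study log linking the participant number" to the person's name.

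The nAb draw is a screening procedure in Protocol 6.1: "Collect blood sample for both nAb against AAV-Spark100 (hemophilia B) and AAV6 (hemophilia A) nAb assessment (central laboratory"). Factor activity, hepatitis, liver fibrosis and HIV tests are repeated "only if there is no documentation within the last 12 months prior to screening (6 months for HCV"). The nAb draw carries no such exemption.

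A note in Protocol 4.4 also covers people who are not screen failures and have a test value "that is outside the range specified by the exclusion criteria, repeated by the central laboratory to determine eligibility".

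Neither document says outright that a person enters the immunity set once, or which result counts if there are two.

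**The concern.** Someone who fails screening on a FibroScan result, say, and returns later has two consents and two numbers. If the nAb sample is drawn and assayed again, both numbers meet the definition in SAP 4.1. A dataset keyed on number would then hold two records for one person.

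Clopper-Pearson assumes independent persons. Duplicates overstate the sample size, and they shift the rate if the people who return differ in nAb status from the rest. The likelier returners are nAb negatives who failed another test, because positives are "subsequently discontinued from further participation in the study". Selective duplication of negatives would pull the rate down.

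The nAb rate is the only estimate in the SAP with a confidence interval, and Protocol 9.5 and SAP 7 foresee publishing nAb status. That makes the question worth asking.

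**Working it through.** **1. Is a second nAb assay planned?** It can be inferred from Protocol 6.1, where nAb lacks the exemption for recent documentation, and from Protocol 7, which names the nAb draw as the only required test. No section states it. Protocol 8.1 describes the screening phase as having a single draw to establish the participant's nAb status. Protocol 4.4 requires that the repeated results be available before baseline; it does not say that every screening test is redone. The inference is possible but not secure.

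**2. Does participant mean person or number?**
- Protocol 4.4: the rescreened participant receives a different number, so the participant stays the same and the number changes.
- Protocol 11.3: one participant-specific code. This is data-protection text and sets no analysis rule.
- SAP 5.3: every member of the immunity set has a nAb status, in the singular.
- SAP 6.3.1: the denominator counts sampled participants, not samples or numbers.

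The ordinary reading is one person, one status.

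**3. Does the note in Protocol 4.4 open a second route?** Hardly. It applies to people not deemed screen failures, whereas Protocol 6.1 has nAb positives discontinued and archived with screen failure as the reason.

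**4. How large could it be?** There is no figure in the plan to reproduce: no prevalence, number assayed, number rescreened or precision target. Assume N = 300 persons and x = 105 positive. If k persons add a second record, the rate becomes (x + k)/(N + k) when all are positive and x/(N + k) when all are negative.

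| Case | Rate | 95% interval | Shift (points) |
|---|---|---|---|
| No duplicates, 105/300 | 35.0% | 29.6 to 40.7 | none |
| 1% (k = 3), negative, 105/303 | 34.7% | 29.3 to 40.3 | -0.3 |
| 1% (k = 3), positive, 108/303 | 35.6% | 30.2 to 41.3 | +0.6 |
| 2% (k = 6), negative, 105/306 | 34.3% | 29.0 to 39.9 | -0.7 |
| 2% (k = 6), positive, 111/306 | 36.3% | 30.9 to 41.9 | +1.3 |

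The half-width without duplicates is (40.7 - 29.6)/2, about 5.5 points. Simulated coverage is 95.5% with no duplicates and 95.2% when 2% are duplicated in proportion to status.

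For an assumed region of 20 persons with 7 positive (35.0%, 15.4 to 59.2), one duplicate gives 7/21 = 33.3% or 8/21 = 38.1%. That is a shift of 1.7 or 3.1 points against a half-width of about 22.

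**5. Wider range.** With 150 to 300 persons, prevalence 30% to 50% and 2% to 10% duplicated, the shift runs from about -4.6 to +6.4 points. The extremes need unlikely inputs. For example, +6.4 arises from 60/165 against 45/150, where 15 of 45 positives (one third) return although positives are discontinued. And -4.6 arises from 75/165 against 75/150, where 15 of 75 negatives (one fifth) return and are assayed again.

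**The case for a change.** The strongest case is practical. Analysts can remove duplicates only if they can recognise them. The one link the protocol describes is the site's log of number to name, and names are not sent to the sponsor. Without a stated rule, nothing obliges anyone to ask. The likelier returners are negatives, so any error would be systematic: duplicating 20 negatives gives 105/320 = 32.8% (27.7 to 38.3), with simulated coverage of about 88%. One or two sentences would close the gap.

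Some of this stands. The SAP has no explicit rule, and the old and new numbers would have to be confirmed with sites. But Protocol 4.4 requires demography and failure details for every screen failure, which is enough to prompt a query that the site log can settle. The 20-negative case needs about one in ten nAb negatives (20 of 195) to be assayed again and left unreconciled, and the documents give no support for that rate.

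A fixed rule is not free of side effects either. If the first sample set nAb status, a person first positive, later rescreened as negative and enrolled would be positive in the immunity table. Yet SAP 4.2 requires nAb negativity for the efficacy set.

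**Conclusion.** No change follows. What is missing is a detail that the documents' own usage already points to: one person, one nAb status. Double counting would need a second assay that is not stated, a dataset keyed on number, and no reconciliation with sites.

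If it did occur at 1% to 2%, the shift would be 0.3 to 1.3 points against a half-width of 5.5, assuming 300 persons and 35% positive. Larger effects need far more rescreening than anything in the documents suggests, but the true number is not given, so this rests on assumption.

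The consequence is limited to an exploratory, descriptive rate. SAP 5.1 plans no hypothesis test. The bleeding and infusion rates are not affected, because the efficacy set also requires entry into the data collection phase. A sentence confirming that each person counts once would be harmless and optional.

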4.2. Efficacy Analysis Set

All participants in the full analysis set who were subsequently identified as nAb negative (negative for nAb to AAV-Spark100 for the hemophilia B cohort, or negative for nAb to AAV6 for the hemophilia A cohort), fulfilled the inclusion/exclusion criteria and who participated in the prospective data collection phase as part of their usual healthcare setting will be included in the efficacy analysis set (Groups B1, B2 and B3 in Figure 2).

Note: With regard to exclusion criterion 2 (Protocol Amendment 8, Section 4.2), any participant with more than 120 days of follow-up and for which the maximum number of days between 2 consecutive FVIII/FIX infusion records represents more than 25% of their follow-up duration will be considered non-compliant with documentation of bleeds and/or prophylaxis replacement therapy administration and will be excluded from the efficacy analysis set.

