4.2. Exclusion Criteria

Participants with any of the following characteristics/conditions will not be included in the study:

1. Anti-AAV-Spark100 neutralizing antibody titer above the established threshold performed by a central laboratory during screening in hemophilia B participants or Anti-AAV6 neutralizing antibody titer above the established threshold performed by a central laboratory during screening in hemophilia A participants.

2. Lack of participant compliance with documentation of bleeds and/or prophylaxis replacement therapy administration.
3. If there is no documentation regarding hepatitis status, as defined below, within the last 12 months prior to screening for hepatitis B and 6 months prior to screening for hepatitis C, then participants will be required to have the following hepatitis testing performed at screening:

- a. **Hepatitis B screening (acute and chronic):**

HBsAg (also referred to as Hepatitis B surface antigen),
HBV-DNA viral assay (also referred to as a nucleic acid test for Hepatitis B virus DNA), and Anti-HBc (also referred to as Total Hepatitis B core antibody).

- a. **Hepatitis B screening (acute and chronic):**
- A participant is not eligible if either HbsAg is positive or HBV-DNA is positive/detectable.
- Anti-HBc must be obtained in all participants for determination of whether the participant had prior hepatitis B. If the anti-HBc is positive and both HBsAg and HBV DNA are negative this would be consistent with a *prior* infection and the participant would be eligible for the study. Anti-HBc must be obtained in all participants to discriminate between those with no prior hepatitis B and those with prior infection in the event of reactivation. FDA has noted reactivation of hepatitis B virus exists.
- One documented negative HBV-DNA viral load is sufficient to assess eligibility. A participant who is currently undergoing anti-viral therapy for hepatitis B is not eligible.

- b. **Hepatitis C (acute or chronic):**

- b. **Hepatitis C (acute or chronic):**
- A participant who is currently undergoing anti-viral therapy for chronic hepatitis C is not eligible.
- Participants treated with anti-viral therapy for chronic hepatitis C, must have completed anti-viral therapy at least 6 months prior to screening and have a negative HCV-RNA at least 6 months prior to screening.

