Neutralizing antibody negative participants will continue with data collection until the End of Study/Early Termination Visit.

Study participants will record their FIX/FVIII replacement therapy administration (date, time, reason for administration, and dose [IU] and bleeding events (date, time, location and whether they are trauma related or spontaneous), in the electronic diary and should reference [Appendix 2](#) as guidance on reporting such events. If bleeding episodes or treatments are not entered or cannot be entered (ie, device left at home by mistake) in the electronic diary during the appropriate time window, data should be entered by the investigator (or site staff member) according to the CRF completion guidelines with required source documentation in the participant's medical record. The reasons for preventative FIX/FVIII replacement therapy will be captured in eCRF. The bleeding episodes and exogenous FIX/FVIII replacement data mentioned above will be referred to as "electronic diary data" regardless of how it is collected (ie, via the handheld device or according to the CRF completion guidelines). It is recommended that the study site review participant compliance on a weekly basis but at a minimum monthly to align with interim phone call to confirm participant compliance with electronic diary entry. The study site should review any change in participant's FIX/FVIII replacement therapy administration, concomitant treatments and report any adverse events (reference [Section 8.1](#) for protocol specified adverse event reporting) in addition to any research related injury adverse event arising through screening blood draw collection. The study site should enter this data in the eCRF accordingly. If necessary, FIX/FVIII inhibitor, FIX/FVIII activity can be done at the investigator's discretion and per their local usual standard of care. Whenever FIX/FVIII activity is assessed, the time (Date/Hour) of

previously administered last dose of FIX/FVIII replacement product or blood product should be captured in the electronic diary as well.

Any unplanned study visits prior to the End of Study/Early Termination Visit will be at the discretion of the investigator and may follow the local usual standard of care. Relevant study related data (FIX/FVIII replacement therapy, bleed events, and/or safety events) generated from an unplanned visit should be entered in the eCRF.

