9.2. Efficacy Analysis

All participants that signed the ICD, were subsequently identified as nAb negative (negative for circulating IgG antibody to AAV-Spark100, or negative for circulating IgG antibody to AAV6) and who participated in the prospective data collection phase as part of their usual healthcare setting will be included in the efficacy analysis set. The cohort of hemophilia B and hemophilia A participants will be analyzed separately.

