3. ENDPOINTS AND BASELINE VARIABLES: DEFINITIONS AND CONVENTIONS

3.1. Primary Endpoint(s)

The primary endpoint is ABR (treated and total). A bleeding episode is defined in Protocol Appendix 2.

If a bleed is treated with FIX infusion (for Hemophilia B) or FVIII infusion (for Hemophilia A) (according to Bleeding eDiary or Bleeding CRF) within 72 hours post the start of bleeding (by comparing date/time of bleeding to date/time of infusion in Infusion eDiary or Infusion CRF), regardless of the type of treatment (preventive, prophylaxis or rescue medication), it will be considered as a treated bleed. If a bleed is not treated with FIX/FVIII infusion according to the Bleeding eDiary or the Bleeding CRF, the bleed will not be considered as a treated bleed but considered as an untreated bleed.

If there are multiple concurrent bleeds (spontaneous or traumatic) on the same date AND time but in different locations in a participant, they will be recorded as one bleed for that participant. If concurrent bleeds occurred on the same day but at different times and different locations, they will be counted as separate bleeds. Only new bleeds (as defined in Protocol Appendix 2) will be counted toward the number of bleeds for ABR calculation.

For untreated bleed, every occurrence will be counted as a separate bleed.

The ABR per participant based on prospectively collected bleeds will be calculated as:

The number of bleeds (all treated bleeding episodes including spontaneous and traumatic) x 365.25 days/number of days during the observation time period while the participant received prophylaxis factor replacement therapy in the usual care setting from baseline visit (Day 1) to end of study (date of study completion or discontinuation, whichever is earlier).

Number of bleeds (treated bleeds and all bleeds, respectively) and infusions within the last 12 months will be collected at the screening visit using hemophilia history CRF for all participants enrolled under Protocol Amendment 5 (01 Oct 2020) or under a subsequent protocol amendment. Thus the retrospectively collected ABR per participant will be equal to number of bleeds in the past 12 months collected in the Hemophilia History form.

Participants enrolled in hemophilia A cohort or hemophilia B cohort prior to Protocol Amendment 5 will not have the CRF retrospectively filled out.

ABR combining retrospective and prospective data will be calculated as:

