4.4. Per-Protocol Analysis Set

All efficacy analysis set participants who have completed at least 6 months of prospective data collection will be included in the per-protocol analysis set (Groups B1 and B2 in Figure 2).

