5.3. Methods to Manage Missing Data

There is no missing data expected for nAb antibody status, since each participant in the immunity analysis set will have a nAb status reported as defined in [Section 4.1](#).

Missing data for endpoints such as ABR, AIR, total consumption of replacement factor will not be imputed for data summaries or listings. No statistical inference will be made.

For the analysis of safety endpoints, no missing data will be imputed unless otherwise specified.

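### The SAP 4.2 diary-compliance rule never tests time before the first or after the last infusion record, so a participant who abandons the diary is kept

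*SAP*

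**What the plan says.** Protocol 4.2, exclusion criterion 2, is "Lack of participant compliance with documentation of bleeds and/or prophylaxis replacement therapy administration", with no number attached. The Note in SAP 4.2 supplies one. A participant with more than 120 days of follow-up counts as non-compliant, and leaves the efficacy set, if the "maximum number of days between 2 consecutive FVIII/FIX infusion records represents more than 25% of their follow-up duration". Neither document gives another numeric test, a convention for the two ends of follow-up, or a rule for 0 or 1 record.

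Other provisions that bear on this:

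- **Denominators.** SAP 3.1 divides bleeds by the "number of days during the observation time period while the participant received prophylaxis factor replacement therapy in the usual care setting", from Day 1 to the date the participant completes or leaves the study. SAP 3.2 does the same for infusions: "observation time period while participant received prophylaxis factor replacement therapy in the usual care setting from baseline visit (Day 1) to end of study". Protocol 9.2.1 and 9.2.2 use Day 1 to end of study without the prophylaxis qualifier.
- **Missing data.** SAP 5.3: "Missing data for endpoints such as ABR, AIR, total consumption of replacement factor will not be imputed".
- **Per-protocol set.** SAP 4.4: "All efficacy analysis set participants who have completed at least 6 months of prospective data collection will be included in the per-protocol analysis set". It adds no compliance test of its own.
- **Protocol efficacy set.** Protocol 9.2 says that nAb-negative participants "who participated in the prospective data collection phase as part of their usual healthcare setting will be included in the efficacy analysis set", with no numeric compliance exclusion.
- **Conduct.** Protocol 6.2 and 6.3 provide for entry by the site "If bleeding episodes or treatments are not entered or cannot be entered (ie, device left at home by mistake) in the electronic diary". Protocol 5.2 and 6.3–6.5 add compliance review at least monthly, calls about every 30 days, diary review at the final visit and discretionary withdrawal.

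**The concern.** The rule is meant to identify people whose diaries cannot be trusted, but it sees only silence that is later broken by another record. Permanent silence is invisible to it, as is a late start. Of two participants with the same silent months, the one who made a single late entry is removed and the one who made none is kept. That is the reverse of what a documentation criterion should do.

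A kept participant still contributes person-time up to completion or discontinuation. Days that stay undocumented add time but no bleeds and no infusions. AIR is then too low if infusions continued, and ABR is too low if bleeds occurred. ABR is the primary endpoint, and Protocol 1.2 makes these data the control for the gene therapy studies. An understated lead-in rate would work against gene therapy there.

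**Working it through.** The plan gives no derivation of the 25% or 120-day limits, so there is no figure to reproduce. The check applies the rule literally to constructed diaries.

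**Inputs from the documents.** The rule applies when follow-up F exceeds 120 days and excludes when longest gap/F > 0.25 (SAP 4.2). The limit is therefore 0.25 × 121 = 30.25 days, 0.25 × 180 = 45 days or 0.25 × 365 = 91.25 days. The least frequent regimen mentioned in Protocol 1.2 is twice per month.

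**Assumptions.** Infusion every 3.5 days (every 14 days for the sparse regimen); F = 180 unless stated; nothing back-entered. Records on days 1, 4.5, …, 57 make 17 records.

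| Diary | As written: longest record-to-record gap / F | With Day 1 and end date as boundaries |
|---|---|---|
| Last record day 57 | 3.5/180 = 1.9%, kept | (180 − 57)/180 = 68.3%, excluded |
| Same, plus one record on day 179 | (179 − 57)/180 = 67.8%, excluded | 67.8%, excluded |
| First record day 90, regular afterwards | 3.5/180 = 1.9%, kept | (90 − 1)/180 = 49.4%, excluded |
| No records | no gap exists, not excluded | (180 − 1)/180 = 99.4%, excluded |
| F = 365, last record day 88.5 | 3.5/365 = 1.0%, kept | (365 − 88.5)/365 = 75.8%, excluded |
| Compliant, every 14 days, F = 121 | 14/121 = 11.6%, kept | 11.6%, kept |

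**Where the contrast begins.** With the last regular record on day 57 of 180, a late record on day 102 gives 45/180 = 25.0% and passes. A record on day 103 gives 46/180 = 25.6% and fails. The reversal therefore needs a late record that closes a gap above the limit.

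**Effect on one participant.** Documented share of time = 57/180 = 0.32. An assumed true ABR of 4 would be reported as 4 × 57/180 = 1.27; for true values of 1 to 8 the range is 0.32 to 2.53. Counting infusions directly, AIR is 17 × 365.25/180 = 34.5 a year against 365.25/3.5 = 104.4, about one third.

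**Effect on the cohort mean.** If affected participants have the same true rate as the others, relative bias ≈ −(share affected × undocumented fraction). All inputs here are assumed:

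| Share affected | 25% undocumented | 50% | 75% |
|---|---|---|---|
| 5% | −1.3% | −2.5% | −3.8% |
| 10% | −2.5% | −5.0% | −7.5% |
| 20% | −5.0% | −10% | −15% |

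This applies to the mean. The median and quartiles, which SAP 6.1.1 also reports, would move differently.

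**The case against.** - **The Note is not the only route to exclusion.** SAP 4.2 separately requires the eligibility criteria to be met, so an abandoner could be removed under criterion 2 by judgement. That is true. But judging silent tails case by case, in an open-label study, while a number governs internal gaps is not a pre-specified rule.
- **Undocumented days may leave the denominator.** SAP 3.1 and 3.2 count time while prophylaxis was received, and the SAP does not say how receipt is established on days without records. If such days were treated as off prophylaxis, the dilution would be smaller. The wording turns on receipt rather than recording, however, and nothing says silent days are dropped.
- **The worked case is a worst case.** Silence from day 57 to day 180 has to survive about four monthly calls, site back-entry, the final diary review and the option of withdrawal. This stands as a limit on frequency and size. It does not change the rule, and withdrawal only brings the end date forward without making the earlier silence count.
- **The cohort range has no support in the documents.** This also stands. In addition, a participant exactly 25% undocumented would still pass a corrected rule, so the first column of the cohort table is not bias the correction removes.
- **The downstream effect is partly out of sight.** This study tests no hypothesis, and whether the gene therapy studies use this efficacy set is decided in plans not available here. The likely direction does not favour the sponsor's product. The primary endpoint of this study should still be estimated correctly.

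**Conclusion.** The rule is wrong as written. It cannot detect silence at either end of follow-up, and it can exclude the better documented of two otherwise identical participants. This follows from the wording alone and does not depend on assumed rates. The per-protocol set inherits the fault.

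The numerical impact is less certain. For an affected participant the loss can be about two thirds of the rate (a factor of 0.32 in the example). That figure assumes that nothing is back-entered, that silent days stay in the denominator, and that infusions and bleeds continued. The cohort effect cannot be estimated from the documents. For undocumented fractions of 50–75%, which a corrected rule would catch if the silence is one unbroken stretch, the assumed range is −2.5% to −15%, and conduct controls would shrink it. The point should be fixed before the final analysis; it does not invalidate the design.

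**What to change.** In SAP 4.2, compute the longest gap over the ordered set of Day 1, all infusion record dates (eDiary or CRF), and the end-of-study or discontinuation date. Keep the 25% limit and the more-than-120-day condition. State explicitly that 0 or 1 infusion record in such a participant is non-compliant.

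Optionally, also report ABR and AIR for the Protocol 9.2 set without the compliance exclusion. This would show how much the rule matters, but it does not itself repair the gap.

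**Cost.** SAP wording and programming only, with dates already collected. A compliant participant on a sparse regimen is safe, as the 11.6% case shows. There may be some further exclusions, including a participant who documented well and then went silent before a late discontinuation date; his earlier valid data would leave the efficacy set. Reporting the set without the exclusion would keep those data visible. Unbroken silence of up to 25% of follow-up would still pass, as the SAP's own tolerance allows.
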